#### Figure 2: Planned L606 Emitted Dose Levels

Clinical laboratory evaluations, physical examination, vital signs, safety 12-lead ECGs, the incidence and severity of AEs, and the incidence of SAEs will be monitored to assess safety and tolerability. A Schedule of Assessments is presented in Appendix 5.

Safety data (in particular those assessments which are considered for dose escalation stopping/dosing stopping criteria; Section 3.7) and PK data (as available) will be reviewed following the completion of each group. Based on this data (as well as aggregate data from previous groups), a decision will be made to proceed with:

- 1) escalation to the next higher planned dose;
- 2) repeat evaluation of the same dose in an additional group;
- 3) evaluation of a lower intermediate dose before moving on to the next higher dose; or
- 4) discontinuation of dosing.

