## 3.7. Dose Escalation Stopping/Dosing Stopping Criteria

If any of the following scenarios occur within a group, dose escalation will be stopped, dose levels will not be repeated, and higher dose levels will not be tested:

• Clinically relevant signs or severe symptoms of similar nature occur in ≥2 subjects within a group, which in the opinion of the safety review team warrant stopping of dose escalation.

- A symptomatic drop in blood pressure from supine to standing of >20 mmHg systolic and/or >10 mmHg diastolic is seen in ≥2 subjects within a group.
- Occurrence of any SAE, which in the opinion of the Principal Investigator, is deemed to be related to study drug.
- Evidence of clinically significant increases in liver function tests (aspartate aminotransferase [AST], alanine aminotransferase [ALT], bilirubin, and gamma glutamyl transferase, defined as ALT or AST >5 × the upper limit of normal [ULN]; or ALT or AST >3 × ULN with a total bilirubin of >2 × ULN with symptoms [ie, monitor for drug-induced liver injury] compared with Day -1) in ≥2 subjects within a group (confirmed with repeat testing).
- Moderate nausea or vomiting that prevents a subject from eating a meal on 3 or more occasions on 2 successive days in ≥2 subjects within a group.
- Symptomatic decrease in supine systolic or diastolic blood pressure of ≥30 or ≥20 mmHg, respectively, from predose baseline in ≥2 subjects within a group.
- Symptomatic decrease in orthostatic systolic or diastolic blood pressure of ≥30 or ≥20 mmHg, respectively, from supine value in ≥2 subjects within a group.
- Forced expiratory volume in 1 second (FEV1) or forced vital capacity (FVC) <65% of predose baseline in ≥2 subjects within a group.
- Symptomatic bronchospasm requiring therapy in  $\geq 2$  subjects within a group.
- Incapacitating dyspnea or coughing, hypoxemia (oxygen saturation ≤90%) in ≥2 subjects within a group.
- Methemoglobin  $\geq 7\%$  in  $\geq 2$  subjects within a group.

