Appendix 5: Schedule of Assessments

# Table 3:Schedule of Assessments

	Screening (Day -28 to Day -2)		Treatment Period			Follow-up Visit
		Check-in (Day -1)	Day 1	Day 2	Discharge (Day 3)	Day 8 to Day 11 (7 to 10 days postdose)
Informed consent	Х					
Demographic data	Х					
Inclusion/exclusion criteria	Х	Х				
Medical history	Х	$X^{a}$				Х
Serology	Х					
Urine drugs of abuse screen (including cotinine)	х	Х				
Alcohol breath or urine test	Х	Х				
Pregnancy test	Х	Х				Х
Study residency						
Check-in		Х				
Discharge					Х	
Nonresidential visit	Х					Х
Dosing with L606 or placebo			Х			
Inhalation administration training b		Х				
Safety and tolerability						
Adverse events c	Х	Х	Х	Х	Х	Х
Concomitant medication	Х	Х	Х	Х	Х	Х
Physical examination d	Х	Х			Х	Х
Body weight, height, and BMI e	Х	Х				
Safety 12-lead ECG f	Х	Х	Х	Х	Х	Х
12-Lead Holter monitor recording g		Х	Х	Х		
Vital signs h	Х	Х	Х	Х	X	Х
Oxygen saturation i		Х		Х	Х	Х
Spirometry j	Х	Х		Х	Х	Х
Clinical laboratory evaluations k	Х	Х		Х	Х	Х
PT, aPTT, INR	Х					
Methemoglobin 	X			Х		
Pharmacokinetics						
Blood sampling for PK analysis of treprostinil m			Х	Х		

Protocol

Abbreviations: AE = adverse event; aPTT = activated partial thromboplastin time; BMI = body mass index; ECG = electrocardiogram; ICF = Informed Consent Form; INR = international normalized ratio; PK = pharmacokinetic; PT = prothrombin time; SAE = serious adverse event.

- a Updated medical history (from Screening).
- b All doses will be self-administered under the supervision of a trained professional in the CRU. Administration instructions and training will be provided and included in separate documents.
- c Between the time of signing the ICF and drug administration, only SAEs will be recorded. All AEs (serious and nonserious) will be recorded as of the time of dose administration until final discharge from the study.
- d Full physical examination at Screening and symptom-directed physical examinations at Check-in, Discharge, and Follow-up.
- e Weight is measured at Screening and Check-in. Height and BMI is measured only at Screening.

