- f Twelve-lead safety ECGs will be collected at Screening; Check-in; Day 1 predose, 4, and 24 hours postdose; Discharge; and Follow-up. Subjects will be required to rest in a supine position for at least 5 minutes prior to the ECG extraction timepoints. Assessment times postdose are relative to the end of the inhalation treatment.
- g Electrocardiogram parameters will be measured using a 24-hour continuous 12-lead Holter monitor beginning the night of Day -1 in order to obtain 8 to 12 hours of predose baseline data, and through 24 hours postdose.
- h Supine blood pressure, supine pulse rate, and respiratory rate will be taken at Screening; Check-in; Day 1 predose and at 0.25, 30, 1, 1.5, 2, 4, 8, 12, and 24 hours postdose; Discharge; and Follow-up. Oral body temperature will be taken at Screening; Check-in; Day 1 predose; Discharge; and Follow-up. Orthostatic vital signs will be assessed at Check-in; Day 1 predose; and at 1, 4, and 8 hours postdose. Assessment times postdose are relative to the end of the inhalation treatment.
- i Oxygen saturation will be measured at rest by standard pulse oximetry Check-in, Day 2, and Discharge.
- j Spirometry (forced expiratory volume in 1 second and forced vital capacity) will be measured in a sitting position, if possible, at Screening, Check-in, Day 2, Discharge, and Follow-up. Pre- and post-bronchodilator spirometry testing will be completed at Screening using albuterol; all other timepoints will not require post-bronchodilator testing.
- k Clinical laboratory evaluations including clinical chemistry, hematology, and urinalysis.
-  Methemoglobin will be measured noninvasively using a finger probe.
- m Blood sampling for PK analysis of treprostinil at Day 1 predose and at 0.25, 0.5, 1, 1.5, 2, 4, 6, 8, 10, 12, 14, 16, and 24 hours postdose. Sampling times postdose are relative to the end of the inhalation treatment.

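### The FEV1/FVC and oxygen-saturation stopping criteria have no scheduled postdose reading on the day of inhalation; a short, silent fall could pass unrecorded

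*Protocol*

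**What the plan says.** Section 3.7 of the Protocol lists 11 criteria, any of which stops escalation. Two of them rest on a respiratory measurement:

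- "Forced expiratory volume in 1 second (FEV1) or forced vital capacity (FVC) <65% of predose baseline in ≥2 subjects within a group"
- "Incapacitating dyspnea or coughing, hypoxemia (oxygen saturation ≤90%) in ≥2 subjects within a group"

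The timing of both measurements is set in Appendix 5, Table 3. The Day 1 cell is empty for spirometry and for oxygen saturation. Footnote j says that spirometry "will be measured in a sitting position, if possible, at Screening, Check-in, Day 2, Discharge, and Follow-up". Footnote i says: "Oxygen saturation will be measured at rest by standard pulse oximetry Check-in, Day 2, and Discharge". Section 7.2.6 sends the reader to the schedule for spirometry times and adds none. Section 7.2.3 does not count oxygen saturation among the vital signs.

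The blood-pressure criteria are served differently. Footnote h times supine readings from 0.25 hours onward and adds: "Orthostatic vital signs will be assessed at Check-in; Day 1 predose; and at 1, 4, and 8 hours postdose".

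Section 3.1 says that the review after each group looks at safety data, "in particular those assessments which are considered for dose escalation stopping/dosing stopping criteria".

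**The concern.** The protocol sets numerical respiratory limits for stopping, but schedules no measurement against them during the day on which the drug is inhaled. Section 1.5 calls this the first human study of L606. Section 1.3 speculates that respiratory toxicity is the one kind the liposomal form might add to what is known of treprostinil. Section 3.5 links peak concentration to local as well as systemic adverse effects.

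Neither the FEV1/FVC limit nor the saturation limit requires symptoms, so each can be met by a change that the subject does not notice. If such a change came and went within Day 1 in two subjects of a group, the review after that group might have no value showing it, and the next dose could be opened. In the first two groups, the same applies to the 48-hour sentinel review before the remaining six subjects are dosed. It would hold Day 2 readings, but no scheduled dosing-day value for these measures.

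**Working it through.** No sample-size, power or error-rate figure bears on this point, so there is no figure of the plan's own to reproduce. The check sets Section 3.7 against Table 3 and its footnotes.

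**1. Scheduled readings by visit (Table 3)**

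| Measure | Screening | Check-in | Day 1 | Day 2 | Discharge | Follow-up | Postdose total |
|---|---|---|---|---|---|---|---|
| Spirometry | X | X | none | X | X | X | 3 |
| Oxygen saturation | none | X | none | X | X | X (not in footnote i) | 3 by the table, 2 by footnote i |

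For both rows the footnote independently omits Day 1, so the empty cells are not an artefact of a broken table. Scheduled Day 1 readings: spirometry 0, oximetry 0.

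**2. Time of the first postdose reading.** The Synopsis equates Day 3 with 48 hours postdose. One day earlier is 48 − 24 = 24 hours. Footnotes f, h and m also set 24-hour ECG, vital-sign and PK times. So the Day 2 spirometry and oximetry fall at about 24 hours. This is an inference, because no clock time is stated for them.

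**3. Criteria affected.** One full criterion of the 11 (FEV1/FVC) and one limb of another (saturation of 90% or below). I read the comma in the latter as *or*, so that low saturation alone counts. The FEV1/FVC limit of 65% of baseline means a fall of more than 100% − 65% = 35%.

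**4. What is scheduled on Day 1.** Footnote h times respiratory rate at 0.25, 30, 1, 1.5, 2, 4, 8, 12 and 24 hours. The 30 is evidently 30 minutes, since the PK list in footnote m has 0.5 hours in that place. That gives eight postdose readings before the 24-hour one. Respiratory rate is not a stopping criterion and measures neither FEV1, FVC nor saturation.

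**5. What can still trigger a stop on Day 1.** Bronchospasm needing therapy, incapacitating dyspnea or coughing, and the general criterion on clinically relevant signs or severe symptoms. An unscheduled spirometry or oximetry reading would also count. Section 3.2 recognises unscheduled assessments, and the Section 3.6 review covers all available data.

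**6. What remains.** Taking steps 1 to 5 together, the uncovered event is a fall past either limit that produces no symptom or sign prompting a reading and has resolved by about 24 hours. The protocol gives neither an incidence nor a recovery time for such an event, so the number missed cannot be calculated.

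**The case against.** The strongest reply is that nothing here is contradictory. Section 3.7 does not promise a Day 1 reading. FEV1 and FVC have a predose value at Check-in and three scheduled postdose readings, so the criterion can be evaluated. A reader might infer that these criteria cannot be met on Day 1 at all. The documents do not support that, because symptom-prompted readings are allowed and would be reviewed. It is true that Sections 7.2.2 to 7.2.4 expressly provide for extra laboratory tests, vital signs and ECGs while Section 7.2.6 has no such sentence for spirometry, but silence is not a prohibition.

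The event is also unlikely. Subjects are healthy, those with asthma or COPD are excluded, inhalation is supervised, and subjects stay in the unit until Day 3 and are asked how they feel at least daily. Respiratory rate is read eight times before 24 hours and could itself prompt a check. Section 3.5 partly points the other way: lower peak concentrations, and fewer clinical findings in rats than with Tyvaso. All of this stands, and it narrows the gap. It does not close it, since each safeguard depends on something visible and the two limits do not.

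A reader might also extend the point to every criterion with an empty Day 1 cell. That goes too far:

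- Methemoglobin is marked only at Screening and Day 2, but the documents give no reason to expect a rise confined to Day 1.
- The liver-function criterion has no Day 1 laboratory test either, and that is of no concern here.

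Finally, a reader might measure the delay from the end of the 8-hour stable plasma level described in Section 3.5. That figure is nonclinical and concerns plasma, not airway effect, so it does not size this gap.

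**Conclusion.** The point holds as a worthwhile, inexpensive improvement to safety monitoring. One full stopping criterion and one limb of another have no scheduled reading on the dosing day; the first comes about 24 hours after inhalation. The exposure is limited to a transient fall in FEV1, FVC or saturation that prompts no reading and is gone by Day 2. Persistent effects would be seen on Day 2 or later, and symptomatic ones are covered elsewhere.

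This rests on two readings of the text: that Day 2 assessments are made at about 24 hours, and that low saturation alone satisfies its criterion. It does not show that the escalation rules are unworkable or that any event would in fact be missed. The difference between Table 3 and footnote i on Follow-up oximetry is clerical.

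**What to change.** Amend Table 3 and footnotes i and j as follows, with final times set by the clinical team.

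- **Oximetry:** add Day 1 postdose readings at existing vital-sign times, including one soon after inhalation, for example 0.5, 1 and 4 hours. Readings at 1 and 4 hours alone would leave the first hour unmeasured.
- **Spirometry:** add one or two Day 1 postdose sessions, for example at about 1 and 4 hours. Under the Section 7 order of events they come after ECG, vital signs and blood collection. Keep them clear of the Holter reading times agreed with the central reader, because Section 7.2.5 asks subjects to avoid activity that could degrade the recording. Check-in spirometry serves as the baseline, so no extra predose session is needed.
- **Optional:** a finger-probe methemoglobin reading at one of the same times.
- **Clerical:** align footnote i with Table 3 on Follow-up oximetry.

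Cost for 64 subjects:

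- Oximetry: 64 × 3 = 192 added readings, taking each subject from 4 to 7 by Table 3 (3 to 6 by footnote i).
- Spirometry: 64 × 2 = 128 added sessions, from 5 to 7 per subject; with one added time, 64 sessions, from 5 to 6.

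Both measurements are already in the study, and the subjects are resident. The real downside is added Day 1 workload and crowding: orthostatic vital signs and a PK sample already fall at 1 and 4 hours, and a safety ECG at 4 hours.

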### 4. SELECTION OF STUDY POPULATION

### 4.1. Inclusion Criteria

Subjects must satisfy all of the following criteria at the Screening visit unless otherwise stated:

- 1. Males or females, of any race, 18 to 50 years of age, inclusive, at Screening.
- 2. Body mass index between 18.5 and  $32.0 \text{ kg/m}^2$ , inclusive, at Screening.
- 3. In good health, determined by no clinically significant findings from medical history, physical examination, 12-lead ECG, vital sign measurements, and clinical laboratory evaluations (congenital nonhemolytic hyperbilirubinemia [eg, Gilbert's syndrome] is not acceptable) at Screening or Check-in as assessed by the Investigator (or designee).
- 4. Ability of the Subject to generate spirometry according to minimum ATS/ERS guidance criteria.
- 5. Females will not be pregnant or lactating, and females of childbearing potential and males will agree to use contraception as detailed in Section 6.6.

- 6. Able to comprehend and willing to sign an ICF and to abide by the study restrictions.
- 7. Agree to abstain from consuming alcohol from 72 hours prior to Check-in.
- 8. Agree to refrain from strenuous exercise from 7 days prior to Check-in.
- 9. Agree to abstain from consuming foods and beverages containing poppy seeds, grapefruit, or Seville oranges from 7 days prior to Check-in.
- 10. Agree to abstain from consuming caffeine-containing foods and beverages from 48 hours prior to Check-in.
- 11. Agree to abstain from consuming carbonated drinks (including sparkling water and soda) from 48 hours prior to Check-in.

#### 4.2. Exclusion Criteria

Subjects will be excluded from the study in the instance of any of the following criteria at the Screening visit unless otherwise stated:

- 1. Clinically relevant abnormalities identified during Screening, physical examination, 12-lead ECG, or laboratory examinations.
- 2. Clinically significant history of hepatic, renal, hematological, pulmonary, cardiovascular, gastrointestinal, neurological, respiratory, endocrine, genitourinary, and/or musculoskeletal disease, glaucoma, a psychiatric disorder, or any other chronic disease, whether controlled by medication or not.
- 3. History of anaphylaxis, significant hypersensitivity, intolerance, or allergy to any drug compound, food, or other substance, unless deemed not clinically significant by the Investigator (or designee).
- 4. History of postural hypotension, unexplained syncope, or hypertension.
- 5. History of asthma, chronic obstructive pulmonary disease (COPD), or reactive airways conditions or findings consistent with asthma or COPD on spirometry testing.
- 6. Blood pressure <90 mmHg systolic or <60 mmHg diastolic after supine at Screening or Check-in upon repeat testing.
- 7. Blood pressure >150 mmHg systolic or >90 mmHg diastolic after supine at Screening or Check-in upon repeat testing.
- 8. Pulse rate >100 bpm after supine for 5 minutes at Screening or Check-in upon repeat testing.
- 9. Have a predisposing condition that could interfere with the absorption, distribution, metabolism, or excretion of drugs.
- 10. Use tobacco- or nicotine-containing products within 6 months prior to Check-in, or have a history of >1 pack cigarettes daily use over multiple years of smoking.
- 11. History of alcoholism or drug/chemical abuse within 2 years prior to Check-in.

- 12. Have a history of alcohol abuse or a history of or current impairment of organ function reasonably related to alcohol abuse.
- 13. Have a history of or current evidence of abuse of licit or illicit drugs or a positive urine screen for drugs of abuse.
- 14. Alcohol consumption of >21 units per week. One unit of alcohol equals 12 oz (360 mL) beer, 1½ oz (45 mL) liquor, or 5 oz (150 mL) wine.
- 15. Positive urine drug screen (including cotinine) at Screening and Check-in or positive alcohol breath or urine test result at Check-in.
- 16. Positive hepatitis panel and/or positive human immunodeficiency virus test at Screening.
- 17. Participation in a clinical study involving administration of an investigational drug (new chemical entity) within 30 days prior to Check-in.
- 18. Use or intend to use any medications/products known to alter drug absorption, metabolism, or elimination processes, including St. John's Wort, within 30 days prior to Check-in, unless deemed acceptable by the Investigator (or designee).
- 19. Use or intend to use any prescription medications/products within 14 days prior to Check-in with the exception of hormone replacement therapy, oral, implantable, transdermal, injectable, or intrauterine contraceptives, unless deemed acceptable by the Investigator (or designee).
- 20. Use or intend to use slow-release medications/products considered to still be active within 14 days prior to Check-in, unless deemed acceptable by the Investigator (or designee).
- 21. Use or intend to use any nonprescription medications/products or herbal supplements within 7 days prior to Check-in, unless deemed acceptable by the Investigator (or designee). Use of nonsteroidal anti-inflammatory drugs or aspirin is prohibited within 14 days prior to Check-in.
- 22. Receipt of blood products within 2 months prior to Check-in.
- 23. Donation of blood or plasma, or the loss of a significant volume of blood (>450 mL) within 6 weeks prior to Screening.
- 24. Poor peripheral venous access.
- 25. Have a history of bleeding problems or abnormal bleeding tendencies.
- 26. Platelet or coagulation factor levels below the lower limit of normal, unless considered not clinically significant by the Investigator.
- 27. Have previously completed or withdrawn from this study or any other study investigating treprostinil, and have previously received the investigational product.
- 28. History of any recent infection within 2 weeks of Check-in.
- 29. In the opinion of the Investigator (or designee), should not participate in this study.

## 4.3. Subject Number and Identification

Subjects will have a unique identification number used at Screening. Subjects will be assigned a subject number prior to the first dosing occasion at the time of their randomization. Assignment of subject numbers will be in ascending order and no numbers will be omitted (eg, Subjects 101, 102, etc.). Replacement subjects (Section 4.4) will be assigned a subject number corresponding to the number of the subject he/she is replacing plus 1000 (eg, Subject 1101 replaces Subject 101).

Subjects will be identified by subject number only on all study documentation. A list identifying the subjects by subject number will be kept in the Site Master File.

### 4.4. Subject Withdrawal and Replacement

A subject is free to withdraw from the study at any time. In addition, a subject will be withdrawn if any of the following criteria are met:

- change in compliance with any inclusion/exclusion criterion that is clinically relevant and affects subject safety as determined by the Investigator (or designee)
- noncompliance with the study restrictions that might affect subject safety or study assessments/objectives, as considered applicable by the Investigator (or designee)
- any clinically relevant sign or symptom that, in the opinion of the Investigator (or designee), warrants subject withdrawal.

If a subject is withdrawn, the Sponsor will be notified and the date and reason(s) for the withdrawal will be documented in the subject's electronic Case Report Form. If a subject is withdrawn, efforts will be made to perform all follow-up assessments, if possible (Appendix 5). Other procedures may be performed at the Investigator's (or designee's) and/or Sponsor's discretion. If the subject is in-house, these procedures should be performed before the subject is discharged from the clinic. The Investigator (or designee) may also request that the subject return for an additional Follow-up visit. All withdrawn subjects will be followed until resolution of all their AEs or until the unresolved AEs are judged by the Investigator (or designee) to have stabilized.

Subjects who are withdrawn for reasons not related to study drug may be replaced following discussion between the Investigator and the Sponsor. Subjects withdrawn as a result of AEs thought to be related to the study drug will generally not be replaced.

### 4.5. Study Termination

The study may be discontinued at the discretion of the Investigator (or designee), Sponsor, or Sponsor's Medical Monitor if any of the following criteria are met:

• AEs unknown to date (ie, not previously reported in any similar investigational study drug trial with respect to their nature, severity, and/or duration)

- increased frequency, severity, and/or duration of known, anticipated, or previously reported AEs (this may also apply to AEs defined at Check-in as baseline signs and symptoms)
- medical or ethical reasons affecting the continued performance of the study
- difficulties in the recruitment of subjects
- cancellation of drug development.

